8.2.3. Electrocardiograms

During the collection of ECGs, participants should be in a quiet setting without distractions (eg, television, cell phones). Participants should rest in a supine position for at least 5 minutes before ECG collection and should refrain from talking or moving arms or legs. If blood sampling or vital sign measurement is scheduled for the same time point as ECG recording, the procedures should be performed in the following order: ECG(s), vital signs, blood draw.

At each time point at which triplicate ECGs are required, 3 individual ECG tracings should be obtained as closely as possible in succession, but no more than 2 minutes apart. The full set of triplicates should be completed in less than 4 minutes.

8.2.4. Clinical Safety Laboratory Assessments

Blood samples for serum chemistry, hematology and coagulation will be collected as noted in Section 10.2, Appendix 2, Clinical Laboratory Tests. The investigator must review the laboratory results, document this review, and record any clinically relevant changes occurring during the study in the adverse event section of the CRF. The laboratory reports must be filed with the source documents.

8.2.4.1. Assessment of Clinical Endpoints

Leukocyte and Platelet Counts

Blood samples will be obtained for measurement of leukocyte and platelet levels at time points specified in the [Schedule of Activities](#).

Hematocrit Concentration

Blood samples will be obtained for the measurement of hematocrit concentration, at time points specified in the [Schedule of Activities](#).

Any participant who has a hematocrit rise with values >20% of the baseline at any timepoint will require full blood count (FBC) monitoring every 4 hours (at the discretion of the investigator).

8.3. Adverse Events, Serious Adverse Events and Other Safety Reporting

Timely, accurate, and complete reporting and analysis of safety information from clinical studies are crucial for the protection of participants, investigators, and the sponsor, and are mandated by regulatory agencies worldwide. The sponsor has established Standard Operating Procedures in conformity with regulatory requirements worldwide to ensure appropriate reporting of safety information; all clinical studies conducted by the sponsor or its affiliates will be conducted in accordance with those procedures.

Adverse events will be reported by the participant (or, when appropriate, by a caregiver, surrogate, or the participant's legally acceptable representative) for the duration of the study. All adverse events and special reporting situations, whether serious or non-serious, will be reported from the time a signed and dated main study ICF is obtained until completion of the participant's last study-related procedure. No AEs will be reported for participants who only signed a pre-screening (diagnostic) ICF and who were not enrolled in the main study.

For further details on adverse events and serious adverse events (Definitions and Classifications; Attribution Definitions; Severity Criteria; Special Reporting Situations; Procedures) as well as product quality complaints, refer to Section 10.4, Appendix 4, Adverse Events: Definitions and Procedures for Recording, Evaluating, Follow-Up, and Reporting.

8.3.1. Time Period and Frequency for Collecting Adverse Event and Serious Adverse Event Information

All Adverse Events

All adverse events and special reporting situations, whether serious or non-serious, will be reported from the time a signed and dated ICF is obtained until completion of the participant's last study-related procedure, which may include contact for follow-up of safety. For participants with only a signed pre-screening (diagnostic) ICF (ie, for whom consent was not given to enroll in the main study by signing the main ICF), no AEs procedure will be reported. Serious AEs, including those spontaneously reported to the investigator within 30 days after the last dose of study intervention, must be reported using the Serious Adverse Event Form. The sponsor will evaluate any safety information that is spontaneously reported by an investigator beyond the time frame specified in the protocol.

Serious Adverse Events

All serious adverse events occurring during the study must be reported to the appropriate sponsor contact person by study-site personnel within 24 hours of their knowledge of the event.

Information regarding serious adverse events will be transmitted to the sponsor using the Serious Adverse Event Form and Safety Report Form of the CRF, which must be completed and reviewed by a physician from the study site and transmitted to the sponsor within 24 hours. The initial and follow-up reports of a serious adverse event should be transmitted electronically or by facsimile (fax).

8.3.2. Method of Detecting Adverse Events and Serious Adverse Events

Care will be taken not to introduce bias when detecting adverse events or serious adverse events. Open-ended and non-leading verbal questioning of the participant is the preferred method to inquire about adverse event occurrence.

Solicited Adverse Events

Signs and symptoms of DENV infection (DENV-infection associated AEs) will be collected by the investigator as solicited AEs. DENV infection signs and symptoms checklist may be compiled by any delegated study team member, and it may be used to assist in the collection of DENV infection associated AEs.

Solicited AEs are predefined events for which the participant is specifically questioned ([Table 2](#)). All AEs are evaluated using the gradings presented in [Table 3](#), the US FDA Toxicity Grading Table in Section [10.6](#), Appendix [6](#), or the rash management protocol in Section [10.7](#), Appendix [7](#).

Table 2: Solicited Adverse Events

| Systemic Reactogenicity | Laboratory Events |
|-----------------------------------|-------------------------------------|
| - Retro-orbital pain ^a | - Decreased Hemoglobin ^b |
| - Abdominal Pain ^a | - Neutropenia ^b |
| - Arthralgia ^a | - Elevated ALT ^b |
| - Fever ^b | - Thrombocytopenia ^b |
| - Headache ^b | - Leukocytosis ^b |
| - Nausea ^b | - Prolonged PT/INR ^b |
| - Fatigue ^b | - Prolonged PTT ^b |
| - Myalgia ^b | |
| - Loss of Appetite ^a | |
| - Vomiting ^b | |
| - Diarrhea ^b | |
| - Rash ^c | |

ALT = alanine aminotransferase; INR = international normalized ratio; PT = prothrombin time; PTT = partial thromboplastin time.

^a Grading according to [Table 3](#)

^b Grading according to the FDA Toxicity Grading Table in Section [10.5](#), Appendix [5](#).

^c Grading according to the rash management protocol in Section [10.7](#), Appendix [7](#).

Table 3: Grading of Solicited Adverse Events

| Local Reaction to Injectable Product | Mild (Grade 1) | Moderate (Grade 2) | Severe (Grade 3) | Potentially Life Threatening (Grade 4) |
|---|--|---|--|--|
| Retro-orbital pain, Arthralgia, Abdominal pain, | Event that is easily tolerated, may require 1 dose of medication/treatment | Event that interferes with daily activity or requires >1 dose of medication/treatment | Event that prevents daily activity | Life-threatening |
| Loss of appetite | Loss of appetite without alteration in eating habits | Oral intake altered without significant weight loss or malnutrition; oral nutritional supplements indicated | Associated with significant weight loss or malnutrition (e.g. inadequate oral caloric intake and/or fluid intake); tube feeding or TPN indicated | Life threatening consequences; urgent intervention indicated |

Unsolicited Adverse Events

Unsolicited adverse events are all adverse events for which the participant is not specifically questioned.

8.3.3. Follow-up of Adverse Events and Serious Adverse Events

Adverse events, including pregnancy, will be followed by the investigator as specified in Section 10.4, Appendix 4, Adverse Events: Definitions and Procedures for Recording, Evaluating, Follow-up, and Reporting.

8.3.4. Regulatory Reporting Requirements for Serious Adverse Events

The sponsor assumes responsibility for appropriate reporting of adverse events to the regulatory authorities. The sponsor will also report to the investigator (and the head of the investigational institute where required) all suspected unexpected serious adverse reactions (SUSARs). The investigator (or sponsor where required) must report SUSARs to the appropriate Independent Ethics Committee/Institutional Review Board (IEC/IRB) that approved the protocol unless otherwise required and documented by the IEC/IRB. A SUSAR will be reported to regulatory authorities unblinded. Participating investigators and IEC/IRB will receive a blinded SUSAR summary, unless otherwise specified.

8.3.5. Pregnancy

All initial reports of pregnancy in female participants or partners of male participants must be reported to the sponsor by the study-site personnel within 24 hours of their knowledge of the event using the appropriate pregnancy notification form. Abnormal pregnancy outcomes (eg, spontaneous abortion, fetal death, stillbirth, congenital anomalies, ectopic pregnancy) are considered serious adverse events and must be reported using the Serious Adverse Event Form. Any participant who becomes pregnant during the study will promptly discontinue further study intervention but will continue study visits for additional safety follow-up.

Follow-up information regarding the outcome of the pregnancy will be required.

8.4. Treatment of Overdose

For this study, any dose of JNJ-64281802 greater than the assigned daily dose within a 24-hour time period will be considered an overdose. The sponsor does not recommend specific intervention for an overdose.

In the event of an overdose, the investigator or treating physician should:

- Contact the Medical Monitor immediately.
- Closely monitor the participant for AE/SAE and laboratory abnormalities until JNJ-64281802 can no longer be detected systemically (at least 46 days).
- Obtain a plasma sample for PK analysis as soon as possible from the date of the last dose of study intervention if requested by the Medical Monitor (determined on a case-by-case basis).
- Document the quantity of the excess dose as well as the duration of the overdosing in the CRF.

Decisions regarding dose interruptions or modifications will be made by the investigator in consultation with the Medical Monitor based on the clinical evaluation of the participant.

8.5. Pharmacokinetics

Venous blood samples will be used to evaluate the PK of JNJ-64281802. Plasma collected for PK may additionally be used to evaluate safety, pharmacokinetic (plasma protein binding, metabolites) or antiviral activity aspects that address concerns arising during or after the study period. Genetic analyses will not be performed on these plasma samples. Participant confidentiality will be maintained.

8.5.1. Evaluations

Venous blood samples will be collected for measurement of plasma concentrations of JNJ-64281802 at timepoints specified in the [Schedule of Activities](#), and processed, handled and identified according to the laboratory manual, which will be provided before the start of the study. The exact dates and times of blood sampling must be recorded in the eCRF or laboratory requisition form.

8.5.2. Analytical Procedures

Plasma samples will be analyzed to determine concentrations of JNJ-64281802 using a validated, specific, and sensitive liquid chromatography-tandem mass spectrometry (LC-MS/MS) method by or under the supervision of the Sponsor's Bioanalytical Laboratory Department of Bioanalysis.

Pharmacokinetic samples from participants receiving placebo will not be analyzed unless unexpected results should occur.

To allow selection of samples, the bioanalytical laboratory will receive randomization lists per treatment. Unblinding of the randomization code will be performed at the bioanalytical laboratory only and will be subjected to a procedure that will ensure that codes will not be revealed to anyone involved in the execution of the study.

If required, some plasma samples may be analyzed to document the presence of circulating metabolites using a qualified research method. In addition, plasma PK samples may be stored for future analysis of protein binding, biomarkers or the metabolite profile.

8.5.3. Pharmacokinetic Parameters and Evaluations

Parameters

The following PK parameters will be derived for JNJ-64281802:

- area under the concentration curve during one dosing interval (AUC_{τ}) (if data allows)
- pre-dose concentration (C_{trough}) and
- maximum observed plasma concentration (C_{max}) (if data allows).

Actual sampling times will be checked for major aberrations. In case a major aberration occurs for an actual sampling time of >20.00% deviation from the scheduled time, this plasma concentration will be excluded from descriptive statistics in the plasma concentration table.

In a subset of 20 participants, total JNJ-64281802 plasma concentration, the fraction unbound (f_u) of JNJ-64281802 and alpha-1 acid glycoprotein may be determined at selected time points, as indicated in the [Schedule of Activities](#) to assess protein binding at the discretion of the sponsor.

Based on the individual plasma concentration-time data, using the actual dose taken and the actual sampling times, PK parameters and exposure information of JNJ-64281802 will be derived.

Pharmacokinetic/Pharmacodynamic Evaluations

Pharmacokinetic-pharmacodynamic evaluations may be performed to evaluate the relationship between the PK and the antiviral activity of JNJ-64281802, as data allow.

In addition, the relationship between the PK and selected safety endpoints may be explored, as data allow and at the discretion of the sponsor.

8.6. Genetics

A blood sample will be collected from all participants for the pharmacogenomic component of the study.

8.6.1. Human Leucocyte Antigen Typing and Pharmacogenomics Assessments

One blood sample for human leucocyte antigen (HLA) typing and for pharmacogenomics (DNA) research will be taken, preferably at baseline (ie, before first dose of study intervention). This sample can be used to determine the HLA type of the participant. In addition, this sample can be used to investigate the potential association of genetic factors with PK, antiviral activity or safety of JNJ-64281802 or the DENV infection.

These analyses may be conducted under the supervision of the sponsor and may be reported separately from the main study report. If necessary, the sample may be collected at a later time point without constituting a protocol deviation.

8.7. Biomarkers

The study includes collection of blood samples for exploratory analysis. Sampling will be performed for all participants at the time points indicated in the [Schedule of Activities](#).

Samples for host RNA might be used for transcriptional profiling for example using microarray technology. Serum samples for protein analyses might be analyzed using assays such as ELISA or Luminex.

Examples of analytes that could be investigated by mRNA assessment and/or protein measurements include, but are not limited to, ISG-15, interleukin (IL)-2, IL-6, IL-8, IL-10, IL-12, IL-15, IL-18, tumor necrosis factor (TNF)- α , IFN- γ , and chemokine (C-X-C motif) ligand 10 (CXCL10, also referred to as interferon-inducible protein 10 [IP-10]).

Samples can only be used for research related to JNJ-64281802 or DENV infection or may be used to develop tests/assays related to JNJ-64281802 or DENV infection.

8.8. Immune Assessments

8.8.1. Humoral Immune Response

Blood samples will be obtained for the assessment of antibody response. Anti-DENV IgG and IgM will be measured using an in-house developed or commercial ELISA and the IgG pattern will be used to make a distinction between primary and secondary dengue infection. Presence of neutralizing antibodies against DENV will be determined using an assay such as flow cytometry-based neutralization assay.

8.8.2. Cellular Immune Response

Peripheral blood mononuclear cell (PBMC) samples may be analyzed in a subset of participants to assess DENV-specific T and B cell immune responses by assays such as enzyme-linked immunospot assay (ELISpot) and/or intracellular cytokine staining (ICS) after stimulation with DENV-specific antigens. ELISpot detects T cells that secrete gamma interferon (IFN- γ) or B cells that secreted IgG and/or IgM in response to an antigenic stimulation, whereas ICS determines the frequency of CD4⁺ and CD8⁺ T cells secreting cytokines such as IFN- γ , interleukin (IL)-2 and tumor necrosis factor (TNF)- α .

Additional experiments may be performed to further phenotypically and functionally characterize PBMCs by flow cytometry or other methods including but not limited to CyTOF, to evaluate innate and adaptive immune responses. Leftover PBMC samples may be used at the sponsor's discretion for additional exploratory research related to DENV infection or JNJ-64281802 (safety/antiviral activity).

9. STATISTICAL CONSIDERATIONS

Statistical analysis will be done by the sponsor or under the authority of the sponsor. A general description of the statistical methods to be used to analyze the antiviral activity and safety data is outlined below. Specific details will be provided in the Statistical Analysis Plan.

9.1. Statistical Hypotheses

The primary hypothesis of this study is that JNJ-64281802 is superior to placebo with respect to reduction in viral load in participants with a primary DENV infection, as measured by area under the log₁₀-transformed DENV RNA viral load curve from baseline on Day 1 until Day 5.

9.2. Sample Size Determination

The study will recruit in total 150 participants, with the primary objective of investigating the antiviral activity of JNJ-64281802 versus placebo based on DENV RNA in primary DENV infection and with an objective to describe the safety and tolerability of JNJ-64281802 in participants with DENV infection. The sample size can be revised after an interim analysis on the proportion of primary versus secondary DENV infections (refer to Section 9.5, Interim Analysis).

For the objective of antiviral activity in participants with a primary DENV infection, the hypothesis is that the intervention effect is superior to placebo as measured on the DENV RNA log₁₀ viral load curve from baseline on Day 1 until Day 5.

To assess sample size requirements for this hypothesis, data of 47 DENV RNA curves were estimated similar to the DENV RNA curves graphically presented in the balapiravir trial. All curves were considered as balapiravir did not have an effect on the viral load. A limit of detection of 2.3 log copies/mL was assumed. Although the majority of the population included in the balapiravir trial suffered from a secondary infection⁰, these estimated DENV RNA curves were considered representative for a primary infected dengue population. As the clearance of DENV RNA occurs earlier and faster in patients with secondary dengue, this is a conservative assumption.⁰

The 47 estimated DENV RNA curves were used to calculate the means, standard deviations and correlations of the log₁₀ viral loads over time. These calculated values were thereafter used to simulate 10,000 trials, each with a sample size of 80 participants. A treatment effect of 0.30 log₁₀ copies/mL per day DENV RNA clearance on top of placebo, or two-fold reduction of the viral load was applied. Based on these 10,000 simulated trials and using a general linear model with treatment regimen as fixed factor and baseline log₁₀ viral load as a covariate, a sample size of 80 participants (40 per group) was estimated to provide a power of at least 80% at the one-sided 5% significance level to detect an intervention effect of 0.30 log₁₀ copies/day additional DENV RNA clearance when compared to placebo.

The specificity of the DENV NS1 testing at baseline is estimated to be 98% which entails that 2% of participants that will be enrolled will not be evaluable for efficacy. Based on literature,⁰ it is estimated that approximately 60% of the total population will have a primary infection. Furthermore, it is anticipated that approximately 4% of the enrolled participants drop-out for other

reasons. The study will therefore need to recruit a total of 150 participants in order to achieve a sample of 84 participants to achieve >80% power on the primary hypothesis.

For the objective of safety assessment, the probability was calculated to observe an (S)AE that has a true incidence of 1% which would be 53% with a total sample size of 75 participants on active treatment; the probability to observe an (S)AE with a true incidence of 0.1%, 0.5% and 0.8% is 7%, 31% and 45%, respectively.

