4. STUDY DESIGN

4.1. Overall Design

This is a randomized, double-blind, placebo-controlled, multicenter, Phase 2a interventional study in participants aged ≥ 18 or ≥ 21 (depending on the legal age of consent in the jurisdiction in which the study is taking place) to ≤ 60 years. Participants who report with an onset of fever of < 48 -hour duration at screening, and who test positive for DENV infection by the NS1 assay will be randomized into the study. Randomization will be stratified by country and by duration of dengue symptoms from onset until the time of randomization (≤ 24 hours and > 24 hours).

The population will include participants with a primary and a non-primary or secondary infection. The difference between the 2 subpopulations will be determined before data base lock and will be based on the IgG profile.

A planned target of 150 male and female participants will be randomly assigned in a ratio of 1:1 to receive JNJ-64281802 or placebo in this study with approximately 75 participants planned per intervention group. The sample size can be revised after an interim analysis on the proportion of primary versus secondary DENV infections (refer to Section 9.5, Interim Analysis).

There are three sequential phases in the study: screening/baseline, double-blind treatment and follow-up. Study participants will complete the screening/baseline visit on Day 0 (predose), followed by a double-blind treatment phase from Day 1 to Day 6 or Day 9 (for participants with dengue warning symptoms). During the double-blind treatment phase, the participants will be admitted to an inpatient facility. At the investigator's discretion, ambulatory visits instead of inpatient treatment can be allowed at Days 3, 4, 5, and 6. All participants will be followed up for a total of 6 months after the first dosing day. The entire study duration for each participant will be approximately 6 months (± 4 days). The participants will complete the study after having completed the final remote follow-up assessment planned 6 months (± 4 days) after having received the first dose of study intervention, unless ongoing adverse events (AEs) require monitoring.

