Mobile clinical teams consisting of trained and delegated site staff (eg, nurses, clinical research coordinators [CRCs]) will visit the clinics and communities to sensitize and pre-screen potential study participants and will play an active role in participant recruitment. Individuals with a suspected DENV infection will be asked to undergo an NS1 rapid test after signing a pre-screening ICF during an ambulatory visit at a health care facility organized by the mobile clinical teams.

The study sites will be open to receive referrals of participants who have consulted a health care facility (eg, clinic/polyclinic, hospital) or practitioner (eg, general practitioner [GP], medical

doctor [MD], nurse) with an onset of fever within the last 48 hours, as reported by the participant, and who tested positive for DENV infection by the NS1 assay at the health care facility. Individuals who test positive during an ambulatory visit or as part of Standard of Care DENV NS1 rapid testing, will be referred to the study site to further coordinate informed consent signing and completion of eligibility assessments. In addition, participants may also report directly to the study site. Participants identified at the study site with an onset of fever as reported by the participant within the last 48 hours, and who test positive for DENV infection by the NS1 assay performed at the site after signing the ICF, will undergo eligibility assessments.

The screening/baseline assessments are to be completed as quickly as possible at the study site. Participants who successfully meet all inclusion criteria and none of the exclusion criteria, will be enrolled and admitted to an inpatient facility. The participants will then be randomized to receive placebo or JNJ-64281802. CCI

Results of screening assessments need to be documented in the electronic case report form (eCRF).

Placebo or JNJ-64281802 will be administered on Days 1 to 5, starting from the day of randomization (Day 1). The participants will stay at the inpatient facility from Day 1 to Day 6 (with an option to attend ambulatory visits on Days 3, 4, 5, and 6 instead at the investigator's discretion) and daily clinical monitoring will be conducted, and blood samples will be collected as shown in [Schedule of Activities](#). Oral intake of food and fluids will be recorded on Days 1, 2, 3, 4, and 5 of dosing.

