5.1. Inclusion Criteria

Each potential participant must satisfy all of the following criteria to be enrolled in the study:

1. Criterion modified per Amendment 1
 - 1.1 Male or female.
2. Criterion modified per Amendment 6
 - 2.1 ≥ 18 or ≥ 21 (depending on the legal age of consent in the jurisdiction in which the study is taking place) to 60 years of age, inclusive, at the time of screening.

3. Must have a body mass index (BMI) between 18 to 35 kg/m² (inclusive) and a body weight of ≥45 kg at screening.
4. Must have a normal 12-lead electrocardiogram (ECG) taken in triplicate at screening (machine read and/or assessed by investigator or cardiologist), including normal sinus rhythm (heart rate between 45 and 100 beats per minute [bpm], extremes included), QTcF ≤450 ms for male participants and ≤470 ms for female participants, QRS interval <110 ms, and PR interval ≤220 ms. If the results of the ECG are outside the normal ranges, the participant may be included only if the investigator judges the deviations from normal to be not clinically significant. This determination must be recorded in the participant's source documents and initialed and dated by the investigator.
5. Criterion modified per Amendment 4
 - 5.1 Patient with a referral note/documentation from a health care facility or practitioner indicating NS1 positive for DENV, positive NS1 rapid test at pre-screening during an ambulatory visit, or patient who tests NS1 positive at the site.
6. Participant reported a fever with an onset within the last 48 hours.
7. Criterion modified per Amendment 4
 - 7.1 Must sign an ICF indicating that he or she understands the purpose of, and procedures required for, the study and is willing to participate in the study. Note: prior to signing the ICF for the study, participants may specifically allow for ambulatory NS1 rapid testing performed by a member of the mobile clinical team by signing the pre-screening ICF.
8. Criterion modified per Amendment 3
 - 8.1 Must sign a separate part of the informed consent form if he or she agrees to provide an optional sample for future exploratory research. Where local regulations require, a separate consent may be requested for the required DNA component of the study.
9. A woman of childbearing potential must have a negative serum pregnancy test at screening.
10. A woman using oral contraceptives should use an additional contraceptive method.

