8.1. Antiviral activity Assessments

At time points specified in the [Schedule of Activities](#), blood samples will be obtained for measurement of:

- levels of DENV RNA
- levels of viremia (ie, infectious virus)
- DENV NS1 protein

Samples may be used by the sponsor for additional assessments analyzing the serologic and virologic characteristics of the DENV infection and antiviral activity of the study intervention, including viral genotypic and phenotypic assessments.

Procedures for sample collection, processing and storage will be provided in the laboratory manual.

DENV RNA levels will be assessed using a validated quantitative DENV RT-PCR assay.

DENV viremia (ie, level of infectious DENV) will be determined using an assay for infectious virus quantification such as a plaque assay.

In addition, antiviral activity will be explored by assessing NS1 protein using an NS1 test. Confirmation of DENV infection will be done retrospectively using qualitative PCR after screening.

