9.3. Populations for Analyses

For purposes of analysis, the following populations are defined:

| Population | Description |
|----------------------------------|--|
| Enrolled | All participants who sign the informed consent form |
| Randomized | All participants who were randomized into the study |
| Safety | All randomized participants who take at least 1 dose of study intervention. |
| PK | All participants who receive at least 1 dose of study drug and who have at least 1 plasma concentration data value after dosing. |
| Intent-to-treat infected (ITT-i) | All randomized participants with a DENV infection who received at least one dose of the study intervention |
| Per-protocol | All participants who are included in the ITT-I population without protocol violations that affect the antiviral activity assessment. |

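### Does reading a 2% non-evaluable share off 98% NS1 specificity undermine the planned 150 participants?

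*Protocol*

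**What the plan says.** Protocol section 9.2 builds the sample size in two steps. First, a simulation of 10,000 trials, each with 80 participants (40 per group), "was estimated to provide a power of at least 80% at the one-sided 5% significance level". Second, 80 is inflated for losses. NS1 specificity is "estimated to be 98% which entails that 2% of participants that will be enrolled will not be evaluable for efficacy", about 60% of the population is expected to have a primary infection, and about 4% are expected to drop out for other reasons. The section concludes that 150 recruits give 84 participants and more than 80% power. The synopsis and SAP section 3 carry the same text.

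Four other provisions bear on the 2%:

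- Section 4.1: people with recent fever "who test positive for DENV infection by the NS1 assay will be randomized into the study".
- Section 5.1: the qualifying result may come from a referral, or be a "positive NS1 rapid test at pre-screening during an ambulatory visit, or patient who tests NS1 positive at the site".
- Section 8.1: "Confirmation of DENV infection will be done retrospectively using qualitative PCR after screening".
- Section 9.3: the ITT-i set is "All randomized participants with a DENV infection who received at least one dose of the study intervention". Section 9.4.2.1 restricts the primary analysis to members of this set with a primary infection.

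On later adjustment, section 9.2 adds: "The sample size can be revised after an interim analysis on the proportion of primary versus secondary DENV infections". Section 9.5 allows an increase if the proportion of primary infections falls below 60%.

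**The concern.** Specificity of 98% means that 2% of uninfected people test positive. It does not mean that 2% of positive tests come from uninfected people. Everyone randomised is NS1-positive, PCR confirmation comes later, and uninfected participants are dropped from ITT-i. The loss to plan for is therefore the chance of being uninfected given a positive test, roughly one minus the positive predictive value (PPV). It can be well above or below 2%, depending on how common dengue is among those tested, and recruitment draws on community pre-screening, referrals and walk-ins. If the true share were much higher, 150 recruits would leave fewer than the 80 participants on which the power statement rests.

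The base for the 60% is also loosely worded. Section 9.2 applies it to the total population, while the sample size review speaks of primary versus secondary infections, which suggests infected participants only. On that second reading, the interim check of the 60% would not by itself reveal an excess of uninfected participants.

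**Working it through.** **Inputs (protocol section 9.2).** N = 150; assumed uninfected share u = 2%; primary infection 60%; other dropout 4%; 80 evaluable for at least 80% power, one-sided 5%.

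**1. Reproduce the plan's figure.**
- Losses multiplied: 150 × (1 − 0.02) × 0.60 × (1 − 0.04) = 84.67.
- Losses subtracted: 150 × 0.60 × (1 − 0.02 − 0.04) = 84.60.

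Both agree with the stated 84. If the 60% already referred to all randomised participants, no separate deduction for the uninfected would be needed: 150 × 0.60 × 0.96 = 86.4, which is also above 84.

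**2. Largest uninfected share that still leaves 80.**
- Multiplied: 150 × 0.60 × 0.96 × (1 − u) = 80, so u = 1 − 80/86.4 = 7.4%.
- Subtracted: u = 1 − 0.04 − 80/90 = 7.1%.
- Without the 4% loss: u = 1 − 80/90 = 11.1%.

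The last line is relevant because ITT-i keeps an infected participant after a single dose (section 9.3), and section 7.1 lets additional participants be entered for those who stop before the last Day 2 dose. Part of the 4% may therefore not be lost, although missing samples would still cost information.

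**3. What the uninfected share could be.** With specificity 0.98,

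1 − PPV = 0.02 × (1 − prev) / [sens × prev + 0.02 × (1 − prev)].

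The documents give neither sensitivity nor prevalence. Taking sensitivity from 1.0 down to 0.5 as an assumption:

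| Prevalence among those tested | Uninfected share among positives |
|---|---|
| 10% | 15% to 27% |
| 20% | 7.4% to 13.8% |
| 30% | 4.5% to 8.5% |
| 50% | 2.0% to 3.8% |
| 80% | 0.5% to 1.0% |

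A share of exactly 2% needs prevalence of about 49.5% to 66%. A share of 7.4% corresponds to about 20% to 33%. The planned 2% is thus possible but not implied, and the error could run in either direction.

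**4. Effect on power.** The protocol gives no standard deviation, so assume that power at 80 is exactly 80%, the least favourable reading of the simulation result. The standardised effect is then (1.645 + 0.842) × √(2/40) = 0.556, and power with n evaluable is Φ(0.556 × √(n/4) − 1.645).

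| Uninfected share | Evaluable | Power |
|---|---|---|
| 2% | 84.7 | 81.9% |
| 5% | 82.1 | 80.9% |
| 7.4% | 80.0 | 80.0% |
| 10% | 77.8 | 79.0% |
| 20% | 69.1 | 74.7% |

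If power at 80 is really 81% or 82%, the break-even share rises to 10.1% or 12.7%.

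**5. What the interim look would show.** Section 9.5 triggers the look at a count of at least 50 primary infections. The planned inputs need about 50/(0.98 × 0.60) = 85 randomised. At an uninfected share of 7.4% the figure is 50/(0.926 × 0.60) = 90. Section 9.4.1 also classifies non-infected participants as a group of their own: about 0.02 × 85 = 1.7 expected in the first case and 0.074 × 90 = 6.7 in the second.

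**The case for a change.** The case for a change is that the inference is false as written and appears three times, including in the SAP, which is the current record of the rationale. The right quantity is known and the correction is a few sentences. At an assumed prevalence of 20% among those tested, the uninfected share would be 7.4% to 13.8%, at or beyond the point where 150 recruits no longer guarantee 80. The interim check does not help if its 60% is counted among infected participants, because it would still read 60%. If the 60% is counted among all randomised, the plan's own inputs give 0.98 × 0.60 = 58.8%, already under the trigger.

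The conceptual error stands, and so does the loose base for the 60%. The claimed consequences are weaker. The simulation gives at least 80% power at 80, so 80 is sufficient but not a demonstrated minimum; an uninfected share above 7.4% leaves the power claim undocumented, not disproved. The low-prevalence rows rest on assumed values, and the documents contain nothing that points to them. The base for the 60% can be inferred: deducting the 2% first and then applying 60% makes sense only among infected participants, and SAP section 3 takes the figure from a trial whose title refers to patients with dengue fever. An analyst at the interim would have had the non-infected group separately classified and would have seen an excess directly. Adding a second proportion, planned at 58.8%, beside an unchanged 60% trigger would more likely confuse than help.

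**Conclusion.** The 2% is an assumption presented as a deduction. It should be read as the planners' guess at the uninfected share among NS1-positive participants, and the 60% as the primary share among infected participants. Read that way, the calculation is coherent and gives 84. The documents support at least 80% power up to an uninfected share of about 7.4% (7.1% with losses subtracted), given the stated 60% and 4%; the margin widens to 11.1% if dropouts stay in ITT-i or are replaced. Even at a 10% share, power would be 79.0% on the least favourable reading of the simulation.

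No change follows because there is nothing to gain. Correcting the sentence would leave the 150, the conduct and every reported output as they are. SAP section 1 records termination for low enrolment after five participants, section 5.3 rules out an efficacy analysis and section 5.6 lists interim analyses as not applicable. Protocol text can be altered only by formal amendment (Appendix 3), which is out of proportion for a flaw in the planning rationale of a stopped trial. The conclusion assumes that the 60% and 4% are about right; sensitivity and prevalence remain unknown.
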